- h. Heart rate, systolic and diastolic blood pressure, respiratory rate, and body temperature. Heart rate and blood pressure measurements should be taken in the supine position and preceded by at least 5 minutes of rest. Vital signs measurements should be performed before blood sampling. Body temperatures will be measured preferably via the oral route.
- i. Investigator must check for acute illness or body temperature \geq 38.0°C/100.4°F at the time of vaccination. If any of these events occur within 24 hours prior to planned vaccination, the vaccination can be rescheduled in alignment with the protocol visit windows. If the vaccination visit cannot be rescheduled within the allowed window or the contraindications to vaccination persist, the reason should be documented. The investigator should also check whether any other reasons for Discontinuation of Study Vaccination have been met.
- j. For women of childbearing potential only.
- k. Whole blood samples will be used for a complete blood count (CBC), including platelet count in a local laboratory or substitute for local laboratory, depending on local feasibility towards turnaround time of sample processing. Serum and plasma samples will be collected and stored for potential future coagulation related testing (including anti PF4) in a central laboratory if the participant experiences an AESI (see Section 10.2, [Appendix 2](#)).
- l. Participants will be observed for a minimum of 15 minutes post vaccination or according to local regulations. Any solicited local (at injection site) and systemic AEs, unsolicited AEs, SAEs, concomitant medications, and vital signs should be documented by study site personnel. Participants will be allowed to leave the study site after the 15 minutes post vaccination observation period is completed and documented.
- m. AEs and special reporting situations that are related to study procedures or vaccine products will be reported from the time a signed and dated ICF is obtained until the end of the study/early withdrawal. Unsolicited AEs should be reported from the time of vaccination until 28 days post vaccination.
- n. All SAEs related to study procedures or vaccine products will be reported from the time a signed and dated ICF is obtained until the end of the study/early withdrawal. All other SAEs are to be reported for all participants from the moment of the first vaccination until the end of the study.

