TTS has been found to resemble heparin-induced thrombocytopenia with thrombosis (HITT), which is mediated by antibodies against complexes of heparin and platelet factor 4 (PF4) that induce Fc receptor-mediated activation of platelets and hypercoagulation ([Arepally 2021](#)). Current evidence suggests that these 2 conditions may be linked ([Streiff 2021](#)). The exact mechanisms remain to be investigated, but anti-PF4 antibodies are suspected to be involved in the pathogenesis of TTS associated with vaccination.

Risks Related to Adenoviral-vectored Vaccines

The sponsor's clinical AdVac® safety database contains pooled safety data from 32 completed and ongoing unblinded clinical studies using the following Ad26-based vaccines: Ad26.ZEBOV (Ebola; 10 studies), Ad26.ENVA.01, Ad26.Mos.HIV, and Ad26.Mos4.HIV (HIV; 8 studies), Ad26.CS.01 (malaria; 1 study), Ad26.RSV.FA2 and Ad26.RSV.preF (RSV; 10 studies), Ad26.Filo (filovirus; 1 study), Ad26.ZIKV.001 (Zikavirus; 1 study), and Ad26.HPV16 and Ad26.HPV18 (HPV; 1 study). A total of 8,152 adult participants (in 32 studies; 2,087 adults aged 18-30 years, 1,738 adults aged 31-50 years, 182 adults aged 51-59 years, and 4,145 adults aged 60 years and older) and 674 children (in 3 studies; 168 children aged 1-3 years, 252 children aged 4-11 years, and 254 children aged 12-17 years) were vaccinated with an Ad26-based vaccine. The total number of Ad26-based vaccine doses administered was 10,867 (10,169 for adults, and 698 for children) administered to 8,826 individuals. Overall, the Ad26-based vaccines were well tolerated, without significant safety issues identified.

Risks Related to Afluria Quadrivalent and FluZone High-dose Quadrivalent

Afluria Quadrivalent is licensed to be used for individuals aged ≥ 6 months and FluZone High-dose Quadrivalent is licensed to be used for individuals aged ≥ 65 years. These seasonal quadrivalent *standard-dose* and *high-dose* influenza vaccines will be administered in the study following the approved prescribing information.

Adverse Reactions Afluria Quadrivalent

In adults 18 to 64 years of age, the most common ($\geq 10\%$) solicited local AR was pain (47.9%); the most common solicited systemic ARs were myalgia (25.5%) and headache (21.7%).

In adults 65 years of age and older, the most common ($\geq 10\%$) solicited local AR was pain (24.6%); the most common solicited systemic AR was myalgia (12.7%).

Adverse Reactions FluZone High-dose Quadrivalent

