- c. Administration of antineoplastic and immunomodulating agents or radiotherapy within 6 months before administration of the first study vaccine and during the treatment period of the study.
- 6. Participant has a history of any neurological disorders or seizures including Guillain-Barré syndrome, with the exception of febrile seizures during childhood.
- 7. Criterion deleted per Amendment 1
- 8. Participant received treatment with immunoglobulins within 3 months or exogenous blood products (autologous blood transfusions are not exclusionary) or blood products within 4 months before the administration of the first study vaccine or plans to receive such treatment during treatment period of the study.

Note: The use of monoclonal antibodies (MABS) before administration of study vaccine and during the study conduct is permitted with the exception of those targeting T cells (anti-CD3, CD4, CD33, and CD52), B cells (anti-CD45, CD19, CD20, CD22, CD27, CD38, and CD138) and check point inhibitors (PD-1, PDL-1 and CTLA-4). Examples of not allowed MABS are: Muromonab-CD3, Gemtuzumab ozogamicin, Alemtuzumab, Bevacizumab, Rituximab, Ofatumumab, Ocrelizumab, Tositumomab, Veltuzumab, Obinutuzumab, Epratuzumab, Pembrolizumab, Nivolumab, Atezolizumab, avelumab, durvalumab and CTLA-4 targeting Ipilimumab. Participants receiving these MABS in the 2 months before the planned administration of the first study vaccine or who plan to receive these MABS during the treatment period of the study will be excluded from participating in the study.

- 9. Participant has history of TTS or heparin-induced thrombocytopenia and thrombosis (HITT).
- 10. Participant has history of capillary leak syndrome.
- 11. Participant received or plans to receive:
 - a. Licensed live attenuated vaccines - within 28 days before or after planned administration of the first or subsequent study vaccines.
 - b. Other licensed (not live) vaccines - within 14 days before or after planned administration of the first or subsequent study vaccines.
- 12. Criterion modified per Amendment 1
 - 12.1 Participant received a licensed/registered SARS-CoV-2 vaccine less than 6 months prior to first study vaccination or during the course of this study (other than study vaccination).
- 13. Participant received vaccination with a seasonal influenza vaccine for the current influenza season in the Northern Hemisphere.

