7. DISCONTINUATION OF STUDY VACCINATION AND PARTICIPANT DISCONTINUATION/WITHDRAWAL

7.1. Discontinuation of Study Vaccination

Study vaccinations will be withheld for the reasons listed below. These participants must not receive any further doses of the study vaccine and could opt for an early termination visit or remain on study for follow-up with assessments of safety and immunogenicity as indicated in the [Schedule of Activities](#). Additional unscheduled visits may be performed for safety/reactogenicity reasons, if needed. In case of questions, the investigator is encouraged to contact the sponsor.

- Any related AE, worsening of health status, or intercurrent illnesses that, in the opinion of the investigator, requires discontinuation from study vaccine
- Unblinding on the participant level that, in the opinion of the sponsor, would compromise the integrity of the data
- Anaphylactic reaction following vaccination, not attributable to causes other than vaccination
- SAE or other potentially life-threatening (Grade 4) event that is determined to be related to study vaccine
- Chronic or recurrent use of systemic corticosteroids at immunosuppressive dose (see Section [6.8](#)), and administration of antineoplastic and immunomodulating agents or radiotherapy
- Withdrawal of consent to receive further study vaccination
- Participant received any experimental medication (including experimental vaccines other than the study vaccine) or receives a licensed/registered COVID-19 vaccine or treatment
- Participant received an influenza vaccine (other than the one administered in the study) for the current influenza season in the Northern Hemisphere
- Participant previously experienced TTS, including CVST or heparin-induced thrombocytopenia (HIT)
- Participant experiences capillary leakage syndrome after the first dose

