10. SUPPORTING DOCUMENTATION AND OPERATIONAL CONSIDERATIONS

10.1. Appendix 1: Abbreviations and Definitions

ACIP	Advisory Committee on Immunization Practices
Ad26	adenovirus type 26
ADCC	antibody-dependent cell-mediated cytotoxicity
AdVAC®	adenoviral vaccine (vector platform)
AE	adverse event
AESI	adverse event of special interest
ANOVA	analysis of variance
aPTT	activated partial thromboplastin time
AR	adverse reaction
ART	anti-retroviral treatment
BMI	body mass index
CD	cluster of differentiation
CDC	Centers for Disease Control and Prevention
CI	confidence interval
CoAd	co-administration
COVID-19	coronavirus disease-2019
CTLA-4	cytotoxic T-lymphocyte-associated antigen 4
CVST	cerebral venous sinus thrombosis
DVT	deep vein thrombosis
eCRF	electronic case report form
eDC	electronic data capture
EEA	European Economic Area
ELISA	enzyme-linked immunosorbent assay
EMA	European Medicines Agency
EU	European Union
EUA	Emergency Use Authorization
FAS	full analysis set
Fc	crystallizable fragment
FDA	Food and Drug Administration
FOIA	Freedom of Information Act
GCP	Good Clinical Practice
GMC	geometric mean concentration
GMT	geometric mean titer
HA	hemagglutinin
HAI	hemagglutinin inhibition assay
HCP	health care professional
HI	hemagglutination inhibition
HIT	heparin-induced thrombocytopenia
HITT	heparin-induced thrombocytopenia with thrombosis
HIV	human immunodeficiency virus
HPV	human papillomavirus
IB	investigator's brochure
ICF	informed consent form
ICH	International Conference on Harmonisation
ICMJE	International Committee of Medical Journal Editors
ICU	intensive care unit
IEC	Independent Ethics Committee
IFN-γ	interferon gamma
Ig	immunoglobulin
IM	intramuscular
IND	Investigational New Drug
IPPI	Investigational Product Preparation Instructions
IRB	Institutional Review Board
IWRS	interactive web response system

MAAE	Medically-attended Adverse Events
MABS	Monoclonal Antibodies
MedDRA	Medical Dictionary for Regulatory Activities
NHP	non-human primate
NI	non-inferiority
PCR	polymerase chain reaction
PCC	protocol clarification communication
PD-1	programmed cell death protein 1
PE	pulmonary embolism
PF-4	platelet factor 4
PI	principal investigator
PPI	per protocol immunogenicity
PPII	per protocol influenza immunogenicity
PPSI	per protocol SARS-CoV-2 immunogenicity
PQC	product quality complaint
PT	prothrombin time
RNA	ribonucleic acid
RSV	respiratory syncytial virus
RT-PCR	real-time reverse-transcriptase polymerase chain reaction
S	Spike
SAE	serious adverse event

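### Entry criterion 9 and the section 7.1 withholding rule list different thrombosis and heparin-related histories, so sites could treat a person with earlier HIT without thrombosis differently

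*Protocol*

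**What the plan says.** Four parts of the protocol bear on this.

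- **Entry (5.2, criterion 9).** "Participant has history of TTS or heparin-induced thrombocytopenia and thrombosis (HITT" is an exclusion. HIT without thrombosis is not mentioned, and neither is CVST by itself.
- **Withholding (7.1).** The section opens with "Study vaccinations will be withheld for the reasons listed below" and continues "These participants must not receive any further doses of the study vaccine". One bullet reads "Participant previously experienced TTS, including CVST or heparin-induced thrombocytopenia (HIT". The bullet after it is "Participant experiences capillary leakage syndrome after the first dose".
- **When 7.1 is checked (1.3.1, footnote i).** The footnote to the pre-vaccination check says "The investigator should also check whether any other reasons for Discontinuation of Study Vaccination have been met". The Schedule places that check before vaccination on both Day 1 and Day 29.
- **Meaning of the terms.** Appendix 1 (10.1) has separate entries for HIT and HITT, the latter being "heparin-induced thrombocytopenia with thrombosis". Section 2.3.1 expands HITT in the same way. Section 8.3.6.1 describes TTS as requiring both a thrombotic event and thrombocytopenia.

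**The concern.** A list that decides who may enter and a list that decides who may be dosed should agree wherever both concern history before the study. Here they use different terms for the heparin-related condition, and the protocol itself distinguishes those terms. The subject is TTS, the trial's single adverse event of special interest, so the wording has safety content.

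What is at stake is consistent conduct. One site might enrol and dose a person with earlier HIT without thrombosis because no criterion names the condition. A second might exclude that person by judgment. A third might randomise the person and then withhold vaccine under 7.1. A participant randomised but never dosed falls outside the Full Analysis Set (9.3), and participants who withdraw are not replaced (6.3).

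**Working it through.** No figure in the plan depends on this point, so there is nothing to reproduce numerically. The check is a comparison of text.

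**Step 1: what each rule covers.** The 7.1 bullet can be read in two ways. On the broad reading, CVST and HIT each count in their own right. On the narrow reading, they count only as instances of TTS as 8.3.6.1 defines it.

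| Earlier history | Criterion 9 | 7.1, broad reading | 7.1, narrow reading |
|---|---|---|---|
| TTS | barred | withheld | withheld |
| HITT (HIT with thrombosis) | barred | withheld | withheld |
| HIT without thrombosis | not named | withheld | not withheld |
| CVST without thrombocytopenia | not named | withheld | not withheld |

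The first two rows agree. The third row is the gap. HIT without thrombosis is not HITT by Appendix 1, and it is not TTS by 8.3.6.1, because the thrombotic event is missing. The fourth row follows the same logic, since thrombocytopenia is missing. It is weaker, because the bullet introduces CVST directly as something included in TTS.

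**Step 2: what each reading implies.** On the broad reading, 7.1 withholds vaccine from people whom no exclusion criterion names. On the narrow reading, coverage nearly matches criterion 9. The bullet then uses HIT to mean only HIT with thrombosis, for which the protocol has a different abbreviation. A site cannot tell from the text which reading is intended.

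**Step 3: whether 7.1 reaches the first dose.** The section title and the reference to further doses suggest participants already vaccinated. Two features point the other way. Footnote i brings the 7.1 reasons into the Day 1 check. The TTS bullet also refers to previous experience with no time limit, whereas the capillary leakage bullet is expressly limited to events after the first dose. Together these favour applying the TTS bullet on Day 1, although the wording is not free of doubt.

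**Step 4: order of the checks.** The Schedule requires eligibility to be settled before randomisation. It marks randomisation and the pre-vaccination check both as Day 1 procedures before vaccination and gives no order between them. The 7.1 check may therefore fall before or after randomisation.

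**Step 5: effect on the analysis.** The documents give no frequency for a history of HIT without thrombosis. I assume that it is rare in adults judged healthy or medically stable. The SAP (section 3) allows about 30 participants per group for exclusions, drop-outs and missing samples, out of about 305 per group (30/305 = 9.8%). A handful of cases would be small against that allowance.

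**The case against.** The strongest reply is that the bullet is not a flat list. It says TTS *including* CVST or HIT, and TTS requires thrombosis. Read that way, 7.1 and criterion 9 cover nearly the same people and all that is left is a loose abbreviation. This stands as a possible reading, and it narrows the conflict. It does not remove it: the reading requires HIT to mean something other than its Appendix 1 entry, and the rule still needs clarifying.

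A reader might also infer four stronger things that the documents do not support.

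- *That such a person is eligible, gets randomised and then must not be dosed.* The text does not fix this sequence. The 7.1 check has no stated position relative to randomisation. Exclusion 16 (significant medical history, in the investigator's opinion) and exclusion 23 (doubt about completing the vaccinations) allow exclusion by judgment. Section 5 also requires questions about the criteria to be resolved with the sponsor before enrolment. These routes are discretionary or general and none names HIT, so they reduce the problem without closing it.
- *That sites cannot comply with both rules.* They can, by not enrolling or not dosing such a person. Criterion 9 obliges no one to vaccinate.
- *That section 2.3.1 supports the wider term.* It compares TTS with "heparin-induced thrombocytopenia with thrombosis (HITT", which is the entity criterion 9 already names.
- *That the wording biases the S-ELISA comparison.* If 7.1 were first noticed on Day 29, a Control participant would lose Ad26.COV2.S and could not enter the PPSI set, while a CoAd participant would lose only placebo. That asymmetry follows from the design and applies to any Day 29 withholding. Here it would also need a rare history, the broad reading and a missed Day 1 check.

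**Conclusion.** The inconsistency is real and is in the current text. Criterion 9 and the 7.1 bullet use different heparin-related terms that the protocol defines separately, and footnote i brings the 7.1 list into the same Day 1 visit at which eligibility is rechecked. On one reading, a history that no exclusion criterion names leads to vaccine being withheld. On the other, 7.1 departs from the protocol's own definitions. Both leave room for sites to act differently.

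It is a minor point about a safety rule, not a threat to the primary result. That judgment rests on two assumptions: that the history is rare, for which the documents give no figure, and that the 7.1 bullet is meant to apply before the first dose, which footnote i supports but the section title leaves open. If the bullet applies only after the first dose, the Day 1 part falls away, but the mismatch at Day 29 remains, because the bullet covers earlier history without a time limit.

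**What to change.** Reconcile criterion 9 in section 5.2 with the TTS bullet in section 7.1 so that one defined list of histories governs both entry and dosing. Use each abbreviation as Appendix 1 defines it, and say whether CVST and HIT count alone or only as part of TTS. State in footnote i, or in 5.2, that this list is checked before randomisation. Which histories belong on the list is a clinical decision for the sponsor, and this review takes no position on it.

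The cost is one line of text in a protocol amendment, or in a clarification communication if the sponsor judges that conduct does not change. Sample size, analysis sets and models are unaffected.

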5.3. Lifestyle Considerations

Potential participants must be willing and able to adhere to the following lifestyle restrictions during the study to be eligible for participation:

1. Refer to Section [6.8](#) for details regarding prohibited and restricted therapy during the study.
2. Agree to follow all requirements that must be met during the study as noted in the Inclusion and Exclusion Criteria (eg, contraceptive requirements).

5.4. Screen Failures

Participant Identification, Enrollment, and Screening Logs

The investigator agrees to complete a participant identification and enrollment log to permit easy identification of each participant during and after the study. This document will be reviewed by the sponsor study site contact for completeness.

The participant identification and enrollment log will be treated as confidential and will be filed by the investigator in the study file. To ensure participant confidentiality, no copy will be made. All reports and communications relating to the study will identify participants by participant identification and age at initial informed consent. In cases where the participant is not randomized into the study, the date and age at initial informed consent will be used.

Individuals who do not meet the criteria for participation in this study (screen failure) may be rescreened once. Participants who are rescreened will be assigned a new participant number, undergo the ICF process, and then restart a new screening phase.

5.5. Criteria for Temporarily Delaying Administration of Study Vaccine

The following events constitute a temporary contraindication to study vaccination:

- Clinically significant acute illness at the time of vaccination. This does not include minor illnesses, such as diarrhea or mild upper respiratory tract infection.
- Fever (body temperature $\geq 38.0^{\circ}\text{C}/100.4^{\circ}\text{F}$) within 24 hours prior to the planned time of vaccination.

If any of these events occur at the scheduled time for the first vaccination, randomization at a later date within the screening window is permitted at the discretion of the investigator and the reason should be documented. If any of these events occur at the scheduled time for one of the subsequent vaccinations, the vaccination visit can be rescheduled, within the allowed windows (see Visit Windows in the [Schedule of Activities](#)).

If the vaccination visit cannot be rescheduled within the allowed window or the contraindications to vaccination persist, the reason should be documented.

6. STUDY VACCINATION AND CONCOMITANT THERAPY

6.1. Study Vaccines Administered

Ad26.COV2.S will be supplied at a concentration of 1×10^{11} vp/mL in single-use vials, with an extractable volume of 0.5 mL, and dosed at 5×10^{10} vp. Placebo (0.9% sodium chloride [NaCl]) will be supplied in single-use vials.

The seasonal influenza vaccines to be used in this study are Afluria Quadrivalent (*standard-dose*) and Fluzone HD Quadrivalent (*high-dose*) or equivalent formulated for the 2021-2022 influenza- season:

- Afluria Quadrivalent (*standard-dose*) is a suspension for IM injection supplied in a 0.5-mL single-dose prefilled syringe. Each dose of Afluria Quadrivalent contains 60 µg of hemagglutinin (HA): 15 µg of each of 4 influenza strains (2 influenza A strains and 2 influenza B strains). For details, refer to the Afluria Quadrivalent package insert.
- Fluzone HD Quadrivalent (*high-dose*) is a suspension for IM injection supplied in a 0.7-mL single-dose prefilled syringe. Each dose of Fluzone HD Quadrivalent contains 240 µg of HA: 60 µg of each of 4 influenza strains (2 influenza A strains and 2 influenza B strains). For details, refer to the Fluzone HD Quadrivalent package insert.

Participants will be vaccinated at the study site according to the schedule shown in [Table 2](#). Study vaccines will be administered by IM injection into the deltoid muscle. On Day 1, each participant will receive 2 IM injections. Each injection should be administered in opposite arms. It is recommended to use the right arm for the seasonal influenza vaccine on Day 1 and the left arm for the Ad26.COV2.S vaccine or placebo on Days 1 and 29.

On Day 29, each participant will receive 1 IM injection, preferably the deltoid muscle of the non-dominant upper arm is used.

If an injection cannot be given in the deltoids due to a medical or other contraindication (for example, tattooed upper arms rendering it difficult to assess site reactogenicity), use alternative locations such as the hip, thigh, or buttocks (to be avoided in overweight participants). When selecting an alternative location, the participant's ability to assess injection site events should be considered. In all circumstances, IM injections in other locations than the upper arm are not considered protocol deviations.

For further information on visit windows see the Schedule of Activities in [Section 1.3.1](#). If a participant cannot be vaccinated within the allowed window, the decision regarding vaccination will be assessed on a case-by-case basis upon discussion between sponsor and investigator. The reason should be documented.

Study vaccine administration must be captured in the electronic case report form (eCRF).

Ad26.COV2.S and placebo will be manufactured and provided under the responsibility of the sponsor. Refer to the IB for a list of excipients ([IB Ad26.COV2.S 2021](#)).

Refer to the study site investigational product and procedures manual (SIPPM) and the Investigational Product Preparation Instructions (IPPI) for additional guidance on study vaccine administration.

Table 3: Description of Interventions

Intervention Name	Ad26.COV2.S	Placebo	Afluria Quadrivalent	Fluzone HD Quadrivalent
Type	Biologic/vaccine	Placebo	Biologic/vaccine	Biologic/vaccine
Dose Formulation	Single-use vials, with an extractable volume of 0.5 mL	Single-use vials, with an extractable volume of 10 mL	0.5 mL single-dose prefilled syringes	0.7 mL single-dose prefilled syringe.
Unit Dose Strength(s)	Ad26.COV2.S at a concentration of 1×10^{11} vp/mL	0.9% NaCl	15 µg HA of each influenza strain	60 µg HA of each influenza strain
Dosage Level(s)	Ad26.COV2.S 5×10^{10} vp once	0.5 mL once	60 µg HA once	240 µg HA once
Route of Administration	IM injection	IM injection	IM injection	IM injection
Use	Experimental	Placebo-comparator	Co-administration	Co-administration
Investigational Medicinal Product (IMP)	Yes	Yes	Yes	Yes
Non-Investigational Medicinal Product/Auxiliary Medicinal Product (NIMP/AxMP)	No	No	No	No
Sourcing	Provided centrally by the Sponsor			
Packaging and Labeling (Labels will contain information to meet the applicable regulatory requirements.)	The study vaccines will be packaged and labeled according to good manufacturing practices and local regulations. The study vaccines will not be packed in individual participant kits, 1 kit will be used by multiple participants. Each kit will contain single-use vials.		The study vaccines will be packaged and labeled according to good manufacturing practices and local regulations. The study vaccines will not be packed in individual participant kits, 1 kit will be used by multiple participants. Each kit will contain single-use vials or prefilled syringes.	
	Not in child resistant packaging			

HA = hemagglutinin; HD = high-dose; IM = intramuscular; vp = virus particles.

